8.2.5. Pregnancy Testing

In this study, a serum pregnancy test will be performed at screening and urine pregnancy tests at subsequent visits as indicated in the SoA (Section 1.3)

8.2.6. Amylase and Lipase Measurements

Serum amylase and lipase measurements will be collected as part of the clinical laboratory testing and as specified in the SoA (Section 1.3). Additional measurements may be performed at the investigator's discretion. Further diagnostic assessments will be recommended as per the algorithm (refer to Appendix 6, Section 10.6) for the monitoring of pancreatic events whenever lipase and/or amylase is confirmed to be $\geq 3x$ ULN at any visit postdose, even if the participant is asymptomatic.

8.2.7. Glucose Monitoring

For safety purposes, blood glucose measurements will be performed using a glucometer with fingerprick capillary blood as specified in the SoA (Section 1.3). Additional blood glucose monitor measurements may also be taken during the study as deemed necessary by the investigator where clinically indicated.

8.2.7.1. Hypoglycemia Reporting

Participants will be trained to recognize the signs, symptoms, and management of hypoglycemia, and to inform the investigator as soon as possible about these events. Participants may, at the investigator's discretion, be given a glucometer to assist in the evaluation of these symptoms.

All hypoglycemic events will be captured in the eCRF as specified below:

- All hypoglycemic episodes will be recorded on a specific eCRF and should not be recorded as AEs unless the event meets severe criteria.
- If a hypoglycemic event meets severe criteria (see definition below), it should be recorded as serious on the AE and SAE eCRFs and reported to Lilly as an SAE.

Investigators should use the following definitions and criteria when diagnosing and categorizing an episode considered to be related to hypoglycemia (the blood glucose values in this section refer to values determined by a laboratory or International Federation of Clinical Chemistry and Laboratory Medicine blood-equivalent glucose meters and strips) in accordance with the 2020 American Diabetes Association position statement on glycemic targets (ADA 2020) as below:

Level 1 Hypoglycemia:

Glucose <70 mg/dL (3.9 mmol/L) and $\geq 54 \text{ mg/dL}$ (3.0 mmol/L): Level 1 hypoglycemia can alert a person to take action such as treatment with fast-acting carbohydrates. Providers should continue to counsel participants to treat hypoglycemia at this glucose alert value.

Level 2 Hypoglycemia:

Glucose <**54 mg/dL (3.0 mmol/L)**: This is also referred to as documented or blood glucose confirmed hypoglycemia with glucose <**54 mg/dL (3.0 mmol/L)**. This glucose threshold is clinically relevant regardless of the presence or absence of symptoms of hypoglycemia.

Level 3 Hypoglycemia:

Severe hypoglycemia (in adults): A severe event characterized by altered mental and/or physical status requiring assistance for treatment of hypoglycemia. For example, participants had altered mental status and could not assist in their own care, were semiconscious or unconscious, or experienced coma with or without seizures; the assistance of another person was needed to actively administer carbohydrate, glucagon, or other resuscitative actions. Glucose measurements may not be available during such an event, but neurological recovery attributable to the restoration of glucose concentration to normal is considered sufficient evidence that the event was induced by a low glucose concentration.

- The determination of a hypoglycemic event as an episode of severe hypoglycemia, as defined above, is made by the investigator based on the medical need of the participant to have required assistance and is not predicated on the report of a participant simply having received assistance.
- If a hypoglycemic event meets the criteria of severe hypoglycemia, the investigator must record the event as serious on the AE CRF and report it to Lilly as an SAE.

Nocturnal Hypoglycemia:

Nocturnal hypoglycemia is a hypoglycemia event (including severe hypoglycemia) that occurs at night and presumably during sleep.

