1.2. Schema

Procedure	Screening		Treatm	ent an	d Safety I	Monitor	ing		-			FU/EDa	Comments
Day	-28 to -2	-1	1	2	3	4	5	6	8	15±1	22±1	29±1	
Informed consent	Х												
Admission to CRU		Х											Enrollment will occur on Day -1
Discharge from CRU							X						May be extended at the investigator's clinical discretion for safety monitoring
Outpatient visits to CRU	Х							x	х	х	х	Х	Days 6, 8, 15±1, and 22±1 may be performed remotely by home health nurses
Review and confirm inclusion/exclusion criteria	Х												
Medical history and demographics	Х												
Physical exam/Medical assessment	Х	X				X			X			x	Screening: Full physical examination All other timepoints: symptom-driven
Height, weight, and BMI	Х	X							Х			Х	Height required only at screening
Temperature	Х		Р										
Safety 12-lead ECG	Х		Р			Х						X	
Vital signs	Х		Р			Х			Х			Х	

1.3. Schedule of Activities (SoA)

Clinical laboratory tests – local laboratory	х		Р						Х			Х	See Appendix 2 (Section 10.2) for details. Predose measures are for baseline purpose only and results need not be reviewed prior to tirzepatide dosing
Ethanol breath test and urine drug screen testing	Х	X											Per CRU local requirements
Pregnancy test	Х	X										Х	Screening: Serum pregnancy test. All other timepoints: urine pregnancy test
AEs/Concomitant Medications	Х	X	Х	Х	X	Х	x	X	X	X	X	Х	
Tirzepatide dosing			0										Actual tirzepatide dosing will be arbitrarily considered as time 0 hour
Tirzepatide plasma PK samples (h)			P, 12	24	48	72	96		168	Х		Х	Predose sample should be collected within 2 hours prior to dosing (time 0)
Glucose safety monitoring (h)			P, 12	24, 36	48	72							Performed using a glucometer using fingerprick capillary blood. Additional unscheduled

						measurements may be taken at the clinical discretion of the investigator

Abbreviations: AE = adverse event; BMI = body mass index; CRU = clinical research unit; D = Day; ECG = electrocardiogram; ED = early discontinuation; FU = follow-up; h = hours; P = predose; PK = pharmacokinetics.

- Note: CRU should schedule procedures as appropriate. However, if multiple procedures take place at the same time point, the following order of the procedure should be considered in terms of prioritization: ECGs, vital signs, PK breastmilk samples, PK plasma samples, clinical laboratory samples, and glucose samples. Unless otherwise specified, predose samples and procedure may be collected or performed any time up to 24 hours prior to dosing.

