8.2.4. Clinical Safety Laboratory Tests

- See Appendix 2 (see Section 10.2) for the list of clinical laboratory tests to be performed and the SoA (see Section 1.3) for the timing and frequency.
- The investigator must review the laboratory results, document this review, and report any clinically relevant changes occurring during the study as an AE. The laboratory results must be retained with source documents unless a Source Document Agreement or comparable document cites an electronic location that accommodates the expected retention duration. Clinically significant abnormal laboratory findings are those which are not associated with the underlying disease unless judged by the investigator to be more severe than expected for the participant's condition.

• All laboratory tests with values considered clinically significantly abnormal during participation in the study should be repeated until the values return to normal or baseline or are no longer considered clinically significant by the investigator or medical monitor.

• If such values do not return to normal or baseline within a period of time judged reasonable by the investigator, the etiology should be identified and the sponsor should be notified.

• All protocol-required laboratory assessments, as defined in Appendix 2 (Section 10.2), must be conducted in accordance with the SoA (Section 1.3), standard collection requirements, and laboratory manual.

• If laboratory values from non-protocol specified laboratory assessments performed at an investigator-designated local laboratory require a change in participant management or are considered clinically significant by the investigator (for example, SAE or AE or dose modification), then report the information as an AE.

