8.3. Adverse Events, Serious Adverse Events, and Product Complaints

The definitions of the following events can be found in Appendix 3 (Section 10.3):

- AEs
- SAEs
- Product complaints

These events will be reported by the participant (or, when appropriate, by a caregiver, surrogate, or the participant's legally authorized representative).

The investigator and any qualified designees are responsible for detecting, documenting, and recording events that meet these definitions and remain responsible for following up on events that are serious, considered related to the study intervention or study procedures, or that caused the participant to discontinue the study intervention (see Section 7).

Care will be taken not to introduce bias when detecting events. Open-ended and nonleading verbal questioning of the participant is the preferred method to inquire about event occurrences.

After the initial report, the investigator is required to proactively follow each participant at subsequent visits/contacts. All SAEs and AEs of special interest (as defined in Section 8.3.3) will be followed until resolution, stabilization, the event is otherwise explained, or the participant is lost to follow-up (as defined in Section 7.3). For product complaints, the investigator is responsible for ensuring that follow-up includes any supplemental investigations as indicated to elucidate the nature and/or causality. Further information on follow-up procedures is provided in Appendix 3 (Section 10.3).

Investigators are responsible for monitoring the safety of participants who have entered this study and for alerting Lilly or its designee to any event that seems unusual even if this event may be considered an unanticipated benefit to the participant.

The investigator is responsible for the appropriate medical care of participants during the study.

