10.2. Appendix 2: Clinical Laboratory Tests

- The tests detailed in the table below will be performed by the local laboratory.
- Additional tests may be performed at any time during the study as determined necessary by the investigator or required by local regulations.
- Investigators must document their review of the laboratory safety results.

Hematology ^a	Clinical Chemistry (fasting) ^a
Hematocrit	Sodium
Hemoglobin	Potassium
Erythrocyte count (RBC)	Bicarbonate
Mean cell volume	Chloride
Mean cell hemoglobin	Calcium
Mean cell hemoglobin concentration	Glucose
Leukocytes (WBC)	Blood urea nitrogen
Platelets	Total protein
Absolute counts of:	Albumin
Neutrophils	Total bilirubin
Lymphocytes	Alkaline phosphatase
Monocytes	Aspartate aminotransferase
Eosinophils	Alanine aminotransferase
Basophils	Creatinine
	Amylase
	Lipase
Urinalysis ^a	
Specific gravity	Hepatitis B surface antigen ^b
pH	Hepatitis C antibody ^b
Protein	HIV or HIV antibody ^b
Glucose	Pregnancy test ^c
Ketones	Ethanol breath test and urine drug screen testing ^d
Bilirubin	Hemoglobin A1Cb
Urobilinogen	
Blood	
Nitrite	
Microscopic examination of sedimente	

Safety Laboratory Tests

Abbreviations: HIV = human immunodeficiency virus; RBC = red blood cells; WBC = white blood cells.

- ^a Performed by local laboratory. Results will be validated by the local laboratory at the time of testing.
- ^b Performed by local laboratory at screening only.
- ^c Pregnancy test: Serum pregnancy test will be performed at screening and urine pregnancy test will be performed at Day -1 and at the safety follow-up, see Schedule of Activities in Section 1.3.
- ^d Performed locally at site during screening and admission on Day -1. Additional testing may be performed at the discretion of the investigator if warranted.
- ^e Test only if urinalysis result is abnormal (i.e., positive for blood, protein, or nitrites).

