10.3.1. Definition of AE

AE Definition

• An AE is any untoward medical occurrence in a participant administered a pharmaceutical product and which does not necessarily have a causal relationship with the study intervention. An AE can therefore be any unfavorable and unintended sign (including an abnormal laboratory finding), symptom, or disease (new or exacerbated) temporally associated with the use of a medicinal (investigational) product, whether or not related to the medicinal (investigational) product.

Events Meeting the AE Definition

- Any abnormal laboratory test results (hematology, clinical chemistry, or urinalysis) or other safety assessments (for example, ECG, radiological scans, vital signs measurements), including those that worsen from baseline, considered clinically significant in the medical and scientific judgment of the investigator (that is, not related to progression of underlying disease).
- Exacerbation of a chronic or intermittent pre-existing condition including either an increase in frequency and/or intensity of the condition.
- New condition detected or diagnosed after study intervention administration even though it may have been present before the start of the study.
- Signs, symptoms, or the clinical sequelae of a suspected drug-drug interaction.
- Medication error, misuse, or abuse of IMP, including signs, symptoms, or clinical sequelae.
- The signs, symptoms, and/or clinical sequelae resulting from lack of efficacy will be reported as AE or SAE if they fulfill the definition of an AE or SAE. Also, lack of efficacy or failure of expected pharmacological action also constitutes an AE or SAE.

Events **NOT** Meeting the AE Definition

- Any clinically significant abnormal laboratory findings or other abnormal safety assessments that are associated with the underlying disease, unless judged by the investigator to be more severe than expected for the participant's condition.
- The disease/disorder being studied or expected progression, signs, or symptoms of the disease/disorder being studied, unless more severe than expected for the participant's condition.
- Medical or surgical procedure (for example, endoscopy, appendectomy): the condition that leads to the procedure is the AE.
- Situations in which an untoward medical occurrence did not occur (social and/or convenience admission to a hospital).

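### Does the protocol leave it open whether a non-severe Level 2 laboratory glucose counts as a treatment-emergent adverse event?

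*Protocol*

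**What the plan says.** **Recording rules.** Protocol 8.2.4 is the general rule for laboratory tests: the investigator must review the results and "report any clinically relevant changes occurring during the study as an AE". Protocol 8.2.7.1 is the rule for hypoglycemia: "All hypoglycemic episodes will be recorded on a specific eCRF and should not be recorded as AEs unless the event meets severe criteria". The same section states that "the blood glucose values in this section refer to values determined by a laboratory" and goes on to include equivalent glucose meters. Of the Level 2 cut-off (below 54 mg/dL) it says: "This glucose threshold is clinically relevant regardless of the presence or absence of symptoms of hypoglycemia".

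**AE definition.** Protocol 10.3.1 counts as AEs "Any abnormal laboratory test results (hematology, clinical chemistry, or urinalysis) or other safety assessments" that the investigator judges clinically significant. Its list of events that are not AEs does not mention non-severe hypoglycemia.

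**Reporting.** Protocol 8.3.3 and SAP 10.4.1 both include Level 2 and Level 3 hypoglycemia among the AEs of special interest (AESIs). SAP 10.4.1 defines a TEAE as a type of AE, so only events recorded as AEs can enter the TEAE tables. SAP 10.4.2 separately lists and summarizes each category of hypoglycemic event.

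**The concern.** Glucose is in the fasting chemistry panel of Protocol Appendix 2, so 8.2.4 reaches it. Section 8.2.7.1 calls the Level 2 threshold clinically relevant, which echoes the trigger words of 8.2.4, and then keeps non-severe episodes off the AE form. Neither section refers to the other or says which prevails.

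If the site applied 8.2.4 to chemistry values and 8.2.7.1 to fingerprick values, the same glucose reading would be a TEAE or not according to how it was measured. The hypoglycemia row of the TEAE table would then be a partial count that disagrees with the SAP 10.4.2 summary. In a study of about 14 women, one reclassified participant is visible in a percentage.

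**Working it through.** The documents give no figure on this point, so there is none to reproduce. The check is how far the two rules overlap, what each reading does to the outputs, and how large the effect could be.

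**1. Scheduled postdose glucose values per woman.** The Schedule of Activities (Protocol 1.3) and the Blood Sampling Summary (10.2.1) agree.
- Fingerprick: 6 samples in all, less 1 predose = 5 (12, 24, 36, 48 and 72 h).
- Chemistry: 3 after screening, less 1 predose = 2 (Days 8 and 29).

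Section 8.2.4 concerns laboratory tests, so only the 2 chemistry values come under it directly. Meter values could enter only through the AE definition in 10.3.1. The ratio 2/7 = 29% counts scheduled tests and does not measure affected events: only a value in the hypoglycemic range can raise the question.

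**2. What each reading does to the outputs for a non-severe Level 2 value.**

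| Reading | AE and TEAE tables | SAP 10.4.2 hypoglycemia summary |
|---|---|---|
| 8.2.7.1 governs all values | Not included | Included |
| 8.2.4 and 10.3.1 govern all values | Included if the investigator judges it clinically relevant or significant | Included |
| 8.2.4 for chemistry, 8.2.7.1 for fingerprick | Chemistry values only | Included |

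The last column does not change, because the instruction to put every episode on the dedicated form conflicts with nothing in 8.2.4. An abnormal chemistry glucose is also summarized with the other chemistry data and flagged in the listings under SAP 10.4.4.

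**3. Which reading the text supports.** Section 8.2.7.1 covers all hypoglycemic episodes and says its values include laboratory ones. The sentence that creates the overlap therefore also brings a Day 8 or Day 29 chemistry value within the specific rule. The third row requires the site to ignore that sentence. Section 8.2.8 shows that recording routes are set event by event: an injection-site reaction goes on the AE form and its dedicated form adds detail, whereas 8.2.7.1 uses the dedicated form in place of the AE form.

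**4. Size.** One woman moved in or out of TEAE incidence changes it by 1/n: 1/14 = 7.1 points with 14 dosed, or 1/8 = 12.5 points with 8. This happens only if she has no other TEAE.

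The documents give no Level 2 rate. If p is the chance that a woman has a non-severe Level 2 value, assumed to be between 1% and 10%, the chance that at least one woman has such a value is 1 − (1 − p)^n:
- n = 14: 1 − 0.99^14 = 13% to 1 − 0.90^14 = 77%.
- n = 8: 1 − 0.99^8 = 8% to 1 − 0.90^8 = 57%.

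These are upper bounds on the chance that TEAE incidence moves. A move also requires that the value be a chemistry one (or a meter value brought in through 10.3.1), that the site depart from 8.2.7.1, and that the woman have no other TEAE.

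**The case for a change.** The strongest case for a change is that the specific-over-general reading does not settle everything. Protocol 8.3.3 and SAP 10.4.1 call Level 2 hypoglycemia an *adverse event* of special interest. Under 8.2.7.1 a non-severe Level 2 event is not on the AE form, and SAP 10.4.1 does not say which form supplies it to the AESI listing. Intensity and causality are required for AEs (Protocol 10.3.4), while for hypoglycemic events SAP 10.4.2 names only the glucose value and treatments, so the AESI listing might mix events with and without a causality assessment. The remedy would be cheap: an exception clause, one SAP sentence and a footnote.

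The mismatch in labels is real and stands. Its consequence is small. SAP 10.4.2 already requires the non-severe Level 2 events to be listed, so an analyst building the AESI listing has an obvious source. Follow-up of AESIs under Protocol 8.3 is tied to the event type in 8.3.3. The causality point is a possibility only, because the form itself is not among the documents. A missing footnote cannot be shown either, because SAP Section 3 places the table layouts in a separate shell document.

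**Conclusion.** The concern does not call for a change. Section 8.2.4 has no written exception for glucose, but 8.2.7.1 is specific, covers laboratory values and gives the site a usable rule. The study has one site (Protocol 4.1), so sites cannot differ. TEAEs are summarized only if their frequency allows (Protocol 9.3.4.1, SAP 10.4.1), and no inferential safety analysis is planned (SAP 10.4.10).

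The most that could happen is a shift of 7.1 points in descriptive TEAE incidence per affected woman with 14 dosed (12.5 with 8). The number affected is unknown and may be zero. The hypoglycemia summary is the same under every reading, no safety data are lost, and the breastmilk AUC is unaffected.

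This conclusion assumes that the site enters all episodes on the hypoglycemia form, as instructed, and that the AESI listing draws non-severe Level 2 events from it. A cross-reference from SAP 10.4.1 to 10.4.2 would be tidy, but it would make no result sounder.

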8.2.8. Injection-Site Reactions

Symptoms and signs of a local injection-site reaction (ISR) may include erythema, induration, pain, pruritus, and edema.

If an ISR is reported by a participant or assessed as clinically significant by CRU personnel, this shall be recorded as an AE and the ISR eCRF will be used to capture additional information about this reaction, such as injection-site pain, degree and area of erythema, induration, pruritus, and edema.

8.2.9. Hypersensitivity Reactions

All hypersensitivity reactions will be reported by the investigator as either AEs or, if any serious criterion is met, as SAEs.

In the event of suspected drug hypersensitivity reactions (immediate or nonimmediate) in participants who experience moderate-to-severe injection reactions as assessed by the investigator, unscheduled blood samples will be collected for PK at the following time points:

- as close as possible to the onset of the event
- at the resolution of the event, and
- $30 (\pm 3)$ days following the event.

Instructions for the collection and handling of blood samples will be provided by the sponsor. The actual date and time (24-hour clock time) of each sampling will be recorded.

8.2.10. Safety Monitoring

The Lilly CP or CRP/scientist will monitor safety data throughout the course of the study.

Lilly will review SAEs within time frames mandated by company procedures. The Lilly CP or CRP/scientist will periodically review

- trends in safety data
- laboratory analytes, and
- AEs.

When appropriate, the Lilly CP or CRP/scientist will consult with the functionally independent Global Patient Safety therapeutic area physician or clinical research scientist.

8.2.10.1. Hepatic Safety

See Appendix 5, Section 10.5 for the full list of hepatic evaluation tests.

Close Hepatic Monitoring

Laboratory tests, including alanine aminotransferase (ALT), aspartate aminotransferase (AST), alkaline phosphatase (ALP), total bilirubin level (TBL), direct bilirubin, gamma-glutamyl transferase, and creatine kinase, should be repeated within 48 to 72 hours to confirm the abnormality and to determine if it is increasing or decreasing if 1 or more of these conditions occur:

If a participant with baseline results of	develops the following elevations:
ALT or AST <1.5x ULN	ALT or AST ≥3x ULN
ALP <1.5x ULN	ALP ≥2x ULN
TBL <1.5x ULN	TBL ≥2x ULN (except for patients with Gilbert's syndrome)
ALT or AST ≥1.5x ULN	ALT or AST $\geq 2x$ baseline
ALP ≥1.5x ULN	ALP ≥2x baseline
TBL≥1.5x ULN	TBL \geq 1.5x baseline (except for patients with Gilbert's syndrome)

Abbreviations: ALP = alkaline phosphatase; ALT = alanine aminotransferase; AST = aspartate aminotransferase; TBL = total bilirubin level; ULN = upper limit of normal.

If the abnormality persists or worsens, clinical and laboratory monitoring and evaluation for possible causes of abnormal liver tests should be initiated by the investigator in consultation with the Lilly-designated CP or CRP/scientist. At a minimum, this evaluation should include a physical examination and a thorough medical history, including symptoms, recent illnesses (for example, heart failure, systemic infection, hypotension, or seizures), recent travel history, history of concomitant medications (including over-the-counter medications), herbal and dietary supplements, history of alcohol drinking, and other substance abuse.

Initially, monitoring of symptoms and hepatic biochemical tests should be done at a frequency of 1 to 3 times weekly based on the participant's clinical condition and hepatic biochemical tests. Subsequently, the frequency of monitoring may be lowered to once every 1 to 2 weeks if the participant's clinical condition and laboratory results stabilize. Monitoring of ALT, AST, ALP, and TBL should continue until levels normalize or return to approximate baseline levels.

Comprehensive Hepatic Evaluation

A comprehensive evaluation should be performed to search for possible causes of liver injury if 1 or more of these conditions occur:

If a participant with baseline results of	develops the following elevations:
ALT or AST <1.5x ULN	ALT or AST \geq 3x ULN with hepatic signs/symptoms ^a , or
	ALT or AST ≥5x ULN
ALP <1.5x ULN	ALP ≥3x ULN
TBL <1.5x ULN	TBL \geq 2x ULN (except for patients with Gilbert's syndrome)
ALT or AST ≥1.5x ULN	ALT or AST $\geq 2x$ baseline with hepatic signs/symptoms ^a , or ALT or AST $\geq 3x$ baseline
ALP ≥1.5x ULN	ALP ≥2x baseline
TBL ≥1.5x ULN	TBL $\geq 2x$ baseline (except for patients with Gilbert's syndrome)

Abbreviations: ALP = alkaline phosphatase; ALT = alanine aminotransferase; AST = aspartate aminotransferase; TBL = total bilirubin level; ULN = upper limit of normal.

^a Hepatic signs/symptoms are severe fatigue, nausea, vomiting, right upper-quadrant abdominal pain, fever, rash, and/or eosinophilia >5%.

At a minimum, this evaluation should include a physical examination and a thorough medical history, as outlined above, as well as tests for prothrombin time-international normalization ratio; tests for viral hepatitis A, B, C, or E; tests for autoimmune hepatitis.

Based on the participant's history and initial results, further testing should be considered, in consultation with the Lilly-designated CP or CRP/scientist, including

- hepatitis D virus
- cytomegalovirus
- Epstein-Barr virus
- acetaminophen levels
- acetaminophen protein adducts
- urine toxicology screen
- Wilson's disease
- blood alcohol levels
- urinary ethyl glucuronide, and
- blood phosphatidylethanol.

Based on the circumstances and the investigator's assessment of the participant's clinical condition, the investigator should consider referring the participant for a

- hepatologist or gastroenterologist consultation
- magnetic resonance cholangiopancreatography
- endoscopic retrograde cholangiopancreatography
- cardiac echocardiogram, or
- liver biopsy.

Additional Hepatic Data Collection (hepatic safety eCRF) in Study Participants Who Have Abnormal Liver Test Results During the Study

Additional hepatic safety data collection in hepatic safety eCRFs should be performed in study participants who meet 1 or more of the following 5 conditions:

- 1. Elevation of serum ALT level to ≥5x ULN on 2 or more consecutive blood tests (if baseline ALT <1.5x ULN)
 - ➤ In participants with baseline ALT ≥1.5x ULN, the threshold is ALT ≥3x baseline on 2 or more consecutive tests.
- 2. Elevated TBL level to ≥2x ULN (if baseline TBL <1.5x ULN) (except for cases of known Gilbert's syndrome)
 - > In participants with baseline TBL $\geq 1.5x$ ULN, the threshold should be TBL $\geq 2x$ baseline.
- 3. Elevation of serum ALP level to ≥2x ULN on 2 or more consecutive blood tests (if baseline ALP <1.5x ULN)
 - ➤ In participants with baseline ALP ≥1.5x ULN, the threshold is ALP ≥2x baseline on 2 or more consecutive blood tests.

- 4. Hepatic event considered to be an SAE.
- 5. Discontinuation of tirzepatide due to a hepatic event.

Note: the interval between the 2 consecutive blood tests should be at least 2 days.

